subject's weight measurement at Visit 3 (prior to dosing for the PK/PD subset), Visit 4 and Visit 5. Treatment can be discontinued or dose modified at any time during the trial. The following symptoms and laboratory abnormalities are considered to be the main guide for decision making concerning treatment discontinuation or dose modifications:

- IGF-1 levels
 - IGF-1 $>+2.0$ SD at any visit should be confirmed by a second measurement measured as soon as possible if deemed clinically significant by the investigator. Blood samples should be collected 5-7 days postdose (TransCon hGH cohort) or at any day (Genotropin cohort). If the IGF-1 SDS is still elevated above $+2.0$, and of clinical concern, the hGH dose may be decreased to the next lower dose bracket for TransCon hGH or a 20% decrease in dose (initially to 0.19 mg hGH/kg/week) for subjects on Genotropin. Any re-establishment of the original dose (0.24 mg hGH/kg/week) due to a subsequent sub-optimal IGF-1 response needs to be discussed with the Medical Expert.
- Glucose parameters:
 - HbA1c $>6.2\%$
 - Fasting glucose level >5.5 mmol/L (100 mg/dL)
 - 2 hour postdose glucose level during OGTT ≥ 7.8 mmol/L (140 mg/dL)

For a subject who had evidence of borderline glucose intolerance or diabetes prior to starting hGH therapy (eg, fasting plasma glucose (FPG) level of 98 mg/dL and HbA1c of 5.9%), it might be appropriate to treat for hyperglycemia as needed, without initial study drug treatment adjustment. However, if a subject with no evidence of glucose intolerance reaches the above glucose parameter levels, the FPG and HbA1c should be repeated within 2-4 weeks. If the repeat values are the same or worse, the TransCon hGH dose may be decreased to the next lower dose bracket ($\sim 20\%$; see Pharmacy Manual), and the dose may be reduced by $\sim 20\%$ for a subject on Genotropin (eg, to 0.19 mg hGH/kg/week or 0.027 mg hGH/kg/day), or appropriate anti-glycemic therapy(ies) may be started. If appropriate follow-up monitoring shows progressively worsening glucose intolerance, additional hGH dose adjustments may be

	
appropriate. If in any case treatment should be discontinued, all subsequent visits and assessments should continue as planned.
 
The Medical Expert will review all AEs on an ongoing basis and all Serious Adverse Event (SAE) reports as received. The key safety data will also be reviewed by an Independent Safety Committee (ISC).


PLANNED NUMBER OF SUBJECTS
	
Approximately 150

TRIAL POPULATION
	
Approximately 150 prepubertal, hGH-treatment naïve children (males and females) with GHD will be included. Subjects will be randomized to 1 of 2 treatment groups in a 2:1 ratio:
 
 • Two thirds of the 150 subjects (approximately 100 subjects) will receive TransCon hGH treatment to obtain an expected 90 evaluable subjects in this cohort • One third of the 150 subjects (approximately 50 subjects) will receive Genotropin treatment to obtain an expected 45 evaluable subjects in this cohort

TRIAL ENTRY CRITERIA
	
Inclusion criteria:
 
 1) Prepubertal children with GHD (either isolated or as part of a multiple pituitary hormone deficiency) in Tanner stage 1 aged: 
 • Boys: 3-12 years, inclusive • Girls: 3-11 years, inclusive 2) Impaired HT defined as at least 2.0 standard deviations (SD) below the mean height for chronological age and sex (HT SDS \leq-2.0) according to the 2000 CDC Growth Charts for the United States Methods and Development or, after approval by the Medical Expert, at least 1.5 SD below the mid-parental height 3) BMI within \pm2.0 SD of the mean BMI for chronological age and sex according to 2000 CDC standards, or BMI within \pm2.0 SD of the mean BMI for bone age and sex 4) Diagnosis of GHD confirmed by 2 different GH stimulation tests, defined as a peak GH level of \leq10 ng/mL, determined with a validated assay. One or 2 well documented historical tests (with properly recorded sampling times and results as well as documented euthyroid status of the subject) performed within approximately 6 months prior to Screening can be accepted to replace 1 or both GH stimulation tests. The highest GH level

	
determines eligibility. For subjects with known panhypopituitarism (eg, subjects who are deficient in TSH and/or ACTH post cranial radiation or born with ≥ 2 pituitary hormone deficiencies in addition to GH), GH stimulation tests may not be required.
 
5) Bone age (BA) at least 6 months less than chronological age (X-ray may have been taken within approximately 6 months prior to Screening, the X-ray or digital image should be sent to the central reader).6) Baseline IGF-1 level of at least 1.0 SD below the mean IGF-1 level standardized for age and sex (IGF-1 SDS ≤ -1.0) according to the central laboratory reference values.7) Normal fundoscopy at Screening (without signs/symptoms of intracranial hypertension).8) Children with multiple hormonal deficiencies must be on stable replacement therapy (stable dose and normal blood hormone levels) for other hypothalamo-pituitary axes for approximately 3 months. Thyroid replacement therapy for thyroid hormone deficiency must be instituted approximately 6 months (and be stable for approximately 3 months) prior to Screening. Temporary adjustment of glucocorticoid replacement therapy, as appropriate, is acceptable.9) Normal 46 XX karyotype for girls (results prior to Screening may be accepted).10) Written, signed informed consent of the parent(s) or legal guardian(s) of the subject and written assent of the subject (if the subject is able to read, understand, and sign). 
Exclusion criteria:
 
1) Children with a body weight below 12 kg2) Prior exposure to recombinant hGH or IGF-1 therapy3) Children with past or present intracranial tumor growth as confirmed by a sellar MRI scan (with contrast dye recommended) at Screening (MRI results from up to approximately 6 months prior to Screening may be accepted)4) Children born small for gestational age (SGA) (ie, birth weight ≤ -2.0 SD for gestational age, with or without a birth length ≤ -2.0 SD for gestational age)
--	--

	
5) Malnutrition, defined as:
 
• Serum albumin level below the lower limit of normal (LLN) according to the reference ranges of the central laboratory, and• Serum iron below the LLN according to the reference ranges of the central laboratory, and• body mass index (BMI) ≤ -2.0 SD for age and sex 
6) Children with psychosocial dwarfism
 
7) Children with idiopathic short stature
 
8) Other causes of short stature such as coeliac disease (confirmed by anti-transglutaminase antibodies test), hypothyroidism, or rickets
 
9) History or presence of malignant disease; any evidence of present tumor growth; children with GHD and clinically cured tumors may be eligible after consultation with the Medical Expert
 
10) Any clinically significant abnormality likely to affect growth or the ability to evaluate growth (eg, chronic diseases like renal insufficiency, spinal cord irradiation)
 
11) Subjects with poorly controlled diabetes mellitus (HbA1c $\geq 8.0\%$) or diabetic complications
 
12) Known chromosomal abnormalities and other named medical syndromes known to impact growth (eg, Turner syndrome, Laron syndrome, Noonan syndrome, Prader-Willi syndrome, Russell-Silver syndrome, SHOX mutations/deletions and skeletal dysplasias) with the exception of septo-optic dysplasia
 
13) Closed epiphyses
 
14) Tanner stage >1 (scant pubic hair alone does not exclude the subject)
 
15) Concomitant administration of other treatments that may have an effect on growth such as anabolic steroids with the exception of hormone replacement therapies (thyroxine, hydrocortisone, desmopressin)
 
16) Children requiring glucocorticoid therapy (eg, asthma) who are taking a dose of greater than 400 $\mu\text{g}/\text{d}$ of inhaled budesonide or equivalents for longer than 1 month during a calendar year

--	---

	
(Note: Approximately equivalent doses: fluticasone: 264 µg/d; beclomethasone: 504 µg/d; flunisolide 1,000 µg/d; triamcinolone: 1,000 µg/d; mometasone: 211 µg/d; ciclesonide 264 µg/d)
 
17) Major medical conditions and/or presence of contraindication to hGH treatment
 
18) Known or suspected HIV-positive subject
 
19) Known hypersensitivity to the components of the study drug
 
20) The subject and/or the parent/legal guardian are likely to be non-compliant with respect to trial conduct
 
21) Participation in any other trial of an investigational agent within 3 months prior to Screening
 
22) Any other reason that in the opinion of the investigator would prevent the subject from completing participation or following the trial schedule

INVESTIGATIONAL PRODUCT
	
Name: TransCon hGH
 
TransCon hGH is a hGH (human Growth Hormone) prodrug that liberates somatropin as the active ingredient through controlled autohydrolysis resulting in sustained release of unmodified somatropin. TransCon hGH consists of recombinant hGH which is transiently conjugated to a PEG molecule through a (TransCon) linker. This conjugation inactivates hGH, thereby creating the TransCon hGH prodrug. After injection of TransCon hGH, autohydrolysis of the linker occurs in a controlled pH- and temperature-dependent manner whereby unmodified, fully active somatropin is released.
 
TransCon hGH will be provided in glass vials and requires reconstitution with 1 mL sterile water for injection, and will be administered by syringe and needle.

REFERENCE PRODUCT(S)
	
Name: Genotropin (somatropin [rDNA origin] for injection)

TREATMENT REGIMENS
	
TransCon hGH
 
TransCon hGH will be administered as once weekly SC injections of 0.24 mg hGH/kg/week.
 
The administration will preferably be in the morning hours, by the trial staff or by the subjects/parents/legal guardians (under supervision by the trial staff at visits where drug administration is

	
foreseen). Only if preferred by a parent/guardian/subject, TransCon hGH administration at home may be once weekly in the evening.
 
Genotropin
 
Genotropin (somatotropin [rDNA origin] for injection) will be administered as daily SC injections in a standard dose of 0.24 mg hGH/kg/week.
 
The total weekly dose will be equally split into 7 daily doses of 0.034 mg hGH/kg/day. A commercially approved injection device will be used for administration of the drug.
 
With the exception of Visit 1 where the injection will be performed in the morning by the trial staff or by the subjects/parents/legal guardians (under supervision by the trial staff), daily administration of Genotropin will preferably be in the evening hours by the parents/legal guardians or subjects. Only if preferred by a parent/guardian/subject, Genotropin administration at home may be once daily in the morning. At some trial visits, trial staff will supervise injections.

PLANNED TRIAL SITES
	
Approximately 100 trial sites in approximately 20 countries in North America, Europe, Middle East and North Africa, and Oceania

CRITERIA FOR EVALUATION
	
Efficacy endpoints:
 
Primary efficacy endpoint: Annualized HV at 52 weeks for weekly TransCon hGH and daily hGH treatment groups
 
Secondary efficacy endpoints:
 
 • Annualized HV for the TransCon hGH and the daily hGH treatment group over 52 weeks • Change in HT SDS over 52 weeks for the TransCon hGH and the daily hGH treatment group • Serum IGF-1 and IGFBP-3 levels and IGF-1 SDS and IGFBP-3 SDS; and normalization of IGF-1 SDS over 52 weeks for the TransCon hGH and the daily hGH treatment group 
Safety endpoints:
 
 • Incidence of AEs • Local tolerability (assessed by the subject, the parents/legal guardians and the investigator)

	
 • Incidence of anti-hGH antibodies including neutralizing antibodies as needed (both cohorts) and incidence of treatment-emergent anti-PEG antibody formation (in TransCon hGH subjects) • IGF-1 levels and IGF-1 SDS • Parameters of glucose metabolism (fasting glucose and insulin level, HbA1c) and lipid parameters • Hormone levels: thyroid status and morning cortisol • All other hematology and biochemistry blood parameters • ECG • Results of the physical examinations, vital sign measurements • Bone age at 52 weeks 
Pharmacokinetic and pharmacodynamic endpoints:
 
Subset of at least 8 TransCon hGH treated subjects after 13 weeks of treatment:
 
 • PK profile of TransCon hGH over 1 week • PK profile of hGH over 1 week • PK profile of PEG over 1 week • PD profile of IGF-1 and IGFBP-3 over 1 week • PD profile of IGF-1 SDS and IGFBP-3 SDS over 1 week • C_{max} for hGH of TransCon hGH

STATISTICAL METHODS
	
Analysis Populations
 
The following data subsets will be analyzed:
 
Safety Analysis Subset – The safety analysis set will include all randomized subjects who have received at least 1 dose of active treatment.
 
Intent-to-treat Subset – The ITT subset will include all randomized subjects who have received at least 1 dose of active treatment and have follow-up efficacy data.
 
Per-protocol Subset – The basis of Per-protocol (PP) subset is the ITT set. Subjects with major protocol deviations will be excluded from the Per-protocol (PP) analysis. Major protocol deviations excluding subjects from the PP analysis set will be defined in the Statistical Analysis Plan (SAP).

PK/PD Population – The PK/PD population includes a subset of subjects from the TransCon hGH cohort who attended Visit 3 as planned and from whom blood sampling was performed at time points predose, 8, 12, 16, 24, 36, 48, 72, 96, 120, and 168 hours postdose.

Efficacy Analysis

The primary endpoint, annualized height velocity at Week 52, will be compared between TransCon hGH treatment and daily hGH treatment, by a non-inferiority comparison with a non-inferiority margin of 2.0 cm/year, followed by a test of superiority if non-inferiority is established.

A mixed model repeated measurement (MMRM) will be the primary analysis to evaluate annualized HV at week 52. The model will include baseline age, peak GH level of the stimulation test, and gender as fixed effects. Least square means will be derived and presented together with 95%-confidence intervals by treatment group.

For the primary efficacy analysis, a 2-sided 95% confidence interval will be calculated for the difference in least square means between the 2 treatment groups [TransCon hGH treatment minus daily hGH] at Week 52. If the lower confidence bound is >-2.0 cm, non-inferiority is demonstrated in terms of effectiveness. If the lower confidence bound is > 0 , superiority is established.

All observed data including post-discontinuation data will be used for the primary analysis. Missing values will be imputed as follows for subjects who prematurely discontinued: From all subjects in the same treatment group who also prematurely discontinued treatment but had a height measurement at Week 52, annualized height change from the last measurement before discontinuation to Week 52 will be calculated. Missing height values at Week 52 will then be imputed by adding the mean change (standardized to the corresponding period between last height measurement and Week 52) to the last height measurement obtained. Based on the imputed height value at Week 52 the corresponding imputed annualized height velocity will be calculated.

The primary efficacy analysis will be performed in the Intent-to-treat set. A sensitivity analysis will be provided for the Per-protocol set.

	
For the continuous secondary efficacy endpoints (height velocity at further visits, change in height SDS, serum IGF-1 levels and IGFBP-3 levels, IGF-1 SDS, IGFBP-3 SDS), similar MMRM models will be used. Two sided 95% confidence intervals will be calculated for the difference in least square means between the 2 treatment groups.
 
The rate of subjects achieving normalization of serum IGF-1 SDS will be calculated by treatment group and visit. A test of superiority in proportion of patients within 0-2.0 IGF-1 SDS will be conducted. A procedure to control for familywise type-1 error of multiple hypothesis testing will be specified in the SAP.
 
In general, for secondary endpoints, missing values will be imputed by a method fully described in the SAP. Moreover, sensitivity analyses concerning missing values for the primary endpoint will be described in the SAP.
 
All efficacy endpoints will be summarized descriptively by treatment group. Additional descriptive summaries may be added by treatment group and randomization stratum, separately for all 3 randomization strata.
 
Figures will be created to display the time course of continuous efficacy endpoints by treatment group.

SAMPLE SIZE DETERMINATION	
This is a pivotal clinical trial intended to support market approval.
 
Based on the phase 2 trial (Protocol ACP-001_CT-004) and similar growth hormone studies published in the literature, and assuming a SD of 3.5 cm/year with a non-inferiority margin of 2.0 cm, a sample size of 147 subjects in the ITT population will be needed to show non-inferiority of TransCon hGH treatment compared to daily hGH with a power of 90%. This sample size calculation is based on a 2:1 randomization and a 1-sided alpha level of 0.025.
 
A sample size of 150 subjects randomized has been chosen to account for slight imbalances in the randomization due to stratification of randomization. For 150 enrolled subjects, approximately 450 subjects may need to be screened in the trial.


TRIAL AND TREATMENT DURATION
	
The total duration of the trial for a subject is expected to be 60 weeks, with up to approximately 6 weeks of Screening and a 52-week active treatment period (plus approximately 2 weeks between randomization and V1).
 
Subjects will be invited to participate in an extension trial after the completion of the initial 52 week treatment period. The intended purpose of the extension period is to assess long-term safety and efficacy. Subjects on Genotropin treatment (Cohort 2) will be switched to TransCon hGH treatment for this extension trial.

---	--

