8.1. Trial Entry Criteria

8.1.1 Inclusion Criteria

Inclusion criteria for this trial are as follows:

- 1) Prepubertal children with GHD (either isolated or as part of a multiple pituitary hormone deficiency) in Tanner stage 1 aged ([Tanner 1976](#)):
 - Boys: 3 -12 years, inclusive
 - Girls: 3 -11 years, inclusive
- 2) Impaired HT defined as at least 2.0 SD below the mean height for chronological age and sex (HT SDS \leq -2.0) according to the 2000 CDC Growth Charts for the United States Methods and Development (www.cdc.gov/growthcharts, [Kuczmarski 2002](#)) or, after approval by the Medical Expert, at least 1.5 SD below the mid-parental height ([Cole 2000](#), [Kriström 2009](#), [Sotos 2014](#)).
- 3) BMI within \pm 2.0 SD of the mean BMI for chronological age and sex according to 2000 CDC standards, or BMI within \pm 2.0 SD of the mean BMI for bone age and sex
- 4) Diagnosis of GHD confirmed by 2 different GH stimulation tests, defined as a peak GH level of \leq 10 ng/mL, determined with a validated assay. One or 2 well documented historical tests (with properly recorded sampling times and results as well as documented euthyroid status of the subject) performed within approximately 6 months prior to Screening can be accepted to replace 1 or both GH stimulation tests. The highest GH level determines eligibility. For subjects with known panhypopituitarism (eg, subjects who are deficient in TSH and/or ACTH post cranial radiation or born with \geq 2 pituitary hormone deficiencies in addition to GH), GH stimulation tests may not be required ([Grimberg 2016](#)).
- 5) Bone age (BA) at least 6 months less than the chronological age (X-ray may have been taken within approximately 6 months prior to Screening, the X-ray or digital image should be sent to the central reader)
- 6) Baseline IGF-1 level of at least 1.0 SD below the mean IGF-1 level standardized for age and sex (IGF-1 SDS \leq -1.0) according to the central laboratory reference values
- 7) Normal fundoscopy at Screening (without signs/symptoms of intracranial hypertension)

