13.2. Sample Size Determination

This is a pivotal clinical trial intended to support market approval.

Based on the phase 2 trial (Protocol ACP-001_CT-004) and similar growth hormone studies published in the literature, and assuming a SD of 3.5 cm/year with a non-inferiority margin of 2.0 cm, a sample size of 147 subjects in the ITT population will be needed to show non-inferiority of TransCon hGH treatment compared to daily hGH with a power of 90%. This sample size calculation is based on a 2:1 randomization and a 1-sided alpha level of 0.025.

A sample size of 150 subjects randomized has been chosen to account for slight imbalances in the randomization due to stratification of randomization. For 150 enrolled subjects, approximately 450 subjects may need to be screened in the trial.

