For categorical variables, the worse case (non-responder) imputation will be applied to impute missing data for ITT analysis.

If growth hormone stimulation data is missing at diagnosis, for example due to structural abnormalities leading to hypopituitarism, a value of 2 ng/mL will be used by convention.

For subjects missing height data for one of the two parents, the average parental height SDS will be estimated based on the non-missing parental height SDS. For subjects with no parental height data, the population median parental height SDS from all subjects with parental height data will be imputed.

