8.1 Primary Efficacy Variable Analysis

The absolute values and mean change from baseline at each timepoint of the annualized height velocity will be presented by treatment group with descriptive statistics.

The primary endpoint, annualized height velocity at week 52, will be compared between TransCon hGH treatment and daily hGH treatment, by a non-inferiority comparison with a non-inferiority margin of 2.0 cm/year, followed by a test of superiority if non-inferiority is established.

As the primary analysis, an ANCOVA model will be used to analyze annualized height velocity at week 52, after potential multiple imputation as described in [Section 6.1.2](#). The annualized height velocity at week 52 will be included in the model as a response variable. The model will include baseline age, peak GH levels (log transformed) at stimulation test, baseline height SDS – average SDS of parental height as covariates, treatment and gender as factors. The estimates from the 100 fitted models for each of the 100 imputed datasets will be combined to provide an overall estimate of the between treatment group difference with a corresponding confidence interval and a p-value.

For the primary efficacy analysis, a 2-sided 95% confidence interval will be calculated for the difference in least square means between the 2 treatment groups [TransCon hGH treatment minus daily hGH] at Week 52. If the lower confidence bound is >-2.0 cm, non-inferiority is demonstrated in terms of effectiveness. If the lower confidence bound is >0 , superiority is established.

Treatment-by-covariate interaction will be examined as appropriate as part of the analysis model examination.

Height velocity at other post-baseline visits will be analyzed similarly using the same ANCOVA model as described above for the primary efficacy analysis. The same ANCOVA model described above will also be used to analyze observed cases as a sensitivity analysis of the primary analysis.

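### The primary ANCOVA's only biochemical severity covariate is peak GH; adding baseline IGF-1 SDS and bone-age delay, already collected for every child, could narrow the interval at almost no cost

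*Protocol*

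**What the plan says.** Protocol Synopsis (Statistical Methods) and 13.4.4 describe a mixed model for repeated measures: "The model will include baseline age, peak GH level of the stimulation test, and gender as fixed effects". Protocol section 13 gives precedence to the final SAP wherever the two differ.

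SAP 8.1 specifies an ANCOVA instead: "The model will include baseline age, peak GH levels (log transformed) at stimulation test", together with baseline height SDS minus average parental height SDS, treatment and gender. The code in SAP 6.1.2.2 has the same five terms. The imputation code in SAP 6.1.2.1 uses the same baseline variables plus the post-baseline heights. Neither contains IGF-1 SDS or bone age.

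**Peak GH.** Protocol 10.1.1 allows any two of five stimulation tests. Protocol 8.1.1 accepts one or two historical results from about the last 6 months and waives testing in known panhypopituitarism. Where stimulation data are missing at diagnosis, SAP 6.1.2.2 says "a value of 2 ng/mL will be used by convention".

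**The two omitted markers.** Protocol 8.1.1 requires "Baseline IGF-1 level of at least 1.0 SD below the mean IGF-1 level standardized for age and sex" and "Bone age (BA) at least 6 months less than the chronological age", with no exception stated for either. IGF-1 is measured at Screening and again at Visit 1 (Protocol 17.2 and 17.3), and SAP 6.1.1 lets Screening stand in when Visit 1 is missing. Bone age goes to a central reader (Protocol 10.1.1). SAP 8.2 uses baseline IGF-1 SDS as a covariate only in models where the outcome is itself an IGF-1 measure. SAP Figure 22 already plots the baseline difference between chronological and bone age.

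**The concern.** Peak GH is a coarse measure of severity under the plan's own rules. Values from different tests are pooled on one scale, some predate Screening, and untested children all receive the same constant. For post-radiation panhypopituitarism, Protocol 10.1.1 allows stimulation tests to be skipped where, among other evidence, IGF-1 is low and bone age is delayed. So for some of the children whose peak GH would carry no information, the protocol leans partly on the two markers that the model leaves out.

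The confidence interval for the height-velocity difference decides both non-inferiority and superiority. A baseline variable that predicts growth beyond the covariates already present would shorten that interval and adjust for chance imbalance between arms of about 100 and 50. Neither IGF-1 SDS nor bone-age delay is a minimization factor (Protocol 7.1.2), so the allocation does not balance them. What is at stake is precision that might be had from data already collected.

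**Working it through.** **Inputs from the documents.** Protocol 13.2: "assuming a SD of 3.5 cm/year with a non-inferiority margin of 2.0 cm"; 90% power; "This sample size calculation is based on a 2:1 randomization and a 1-sided alpha level of 0.025"; 147 in the ITT population; 150 randomized, so 100 and 50.

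**Assumptions.** The true difference is 0 for the sample size. The 3.5 is taken as the residual SD under the current covariates, which Protocol 13.2 does not say. R² is the share of that residual variance explained by the two added terms; no value is given, so a range is used.

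**Step 1: the plan's own figure.** Control-arm n = (1 + 1/2) × (1.960 + 1.282)² × 3.5² / 2.0² = 1.5 × 10.507 × 3.0625 = 48.3, rounded up to 49. The test arm is 98, total 147. This reproduces. A noncentral-t check gives power of 90.0% at 49:98 and 90.6% at 50:100. The sample size is not in question.

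**Step 2: expected half-width under the SAP model.** With n = 150 and k fixed-effect parameters including the intercept,

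half-width = t(0.975, n − k) × 3.5 × √(1/100 + 1/50) × √(1 − R²) × √(1 + (k − 2)/(n − k − 2)).

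The last factor is the expected loss from chance imbalance in the k − 2 adjusting covariates. The SAP model has k = 6 (intercept, treatment, gender, age, log peak GH, height SDS minus parental SDS):

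1.9766 × 0.6062 × √(1 + 4/142) = 1.9766 × 0.6062 × 1.0140 = 1.215 cm.

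**Step 3: add the two terms.** With k = 8 and R² = 0:

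1.9768 × 0.6062 × √(1 + 6/140) = 1.9768 × 0.6062 × 1.0212 = 1.224 cm.

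Multiplying by √(1 − R²) gives the rest. The last column is 150 × [(1.215 / new half-width)² − 1].

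| Assumed R² | Half-width (cm) | Change | Equivalent extra children |
|---|---|---|---|
| 0 | 1.224 | +0.7% | −2 |
| 1.4% | 1.215 | about 0 | 0 |
| 5% | 1.193 | −1.8% | 6 |
| 10% | 1.161 | −4.4% | 14 |
| 15% | 1.128 | −7.1% | 24 |

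The break-even follows from Step 3: 1 − (1.2150/1.2238)² = 0.014.

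**Step 4: what this means for the tests.** By normal approximation at 100:50, ignoring the small cost in degrees of freedom, non-inferiority power goes from 91.0% to 92.3% (R² 5%) or 93.5% (10%). At an assumed true difference of 1.0 cm/year, superiority power goes from 37.8% to 39.5% or 41.2%.

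**The case against.** The strongest reply is that this is a preference about covariates with no demonstrated benefit. Nothing in either document relates IGF-1 SDS or bone-age delay to height velocity. The entry cut-offs (IGF-1 SDS at or below −1.0, bone age at least 6 months behind) restrict the range of both, and both may overlap with age, peak GH and height deficit. The gain is also small in absolute terms: 0.02 cm at R² 5% and 0.09 cm at 15%, against a margin of 2.0 cm. All of this stands, and it is why the size is given as a range.

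The proposed markers are not free of peak GH's weaknesses. The bone-age film may also be up to about 6 months old at Screening. In its section on the PK/PD subset, the SAP sets IGF-1 below the quantitation limit to that limit before the SDS is computed (11.1.3). The SAP's use of baseline IGF-1 SDS in IGF-1 models says nothing about its value for height velocity, because there it is the baseline of the outcome. Peak GH, age and gender are minimization factors, so adjusting for them follows the design. These points stand too. They argue for keeping peak GH, and the proposal does keep it.

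A reader might infer three stronger things that the documents do not support:

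- **That peak GH is the model's only measure of severity.** The protocol's list suggests this, but the SAP is the analysis of record and adds baseline height SDS minus average parental height SDS, a measure of growth deficit. The statement holds only for biochemical markers.
- **That precision is being lost.** Without an R² this cannot be shown. Below about 1.4% the interval would widen slightly.
- **That the comparison is biased or underpowered.** Omitting a prognostic covariate does not bias a randomized comparison, and the stated 147 reproduces.

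**Conclusion.** The concern holds as a minor efficiency point. The primary ANCOVA relies on a heterogeneous peak GH as its only biochemical severity marker and leaves out two markers that every child must have to enter. The trade is asymmetric: at worst a half-width about 0.7% wider (0.01 cm), against 1.8% to 7.1% narrower if the two terms explain 5% to 15% of residual variance. The result rests on 3.5 cm/year being the residual SD under the current covariates, on 100 and 50 analysed children, and on the assumed R² values. The change cannot be justified as correcting an error. Confidence in the size of the gain is low.

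**What to change.** Before unblinding, keep all the present covariates and add two to the primary ANCOVA in SAP 6.1.2.2 and 8.1, and to its per-protocol and observed-case repeats:

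- baseline IGF-1 SDS (Visit 1, with Screening as the fallback under SAP 6.1.1);
- bone-age delay, defined as chronological age minus centrally read bone age, both at the date of the film.

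Adding the same two variables to the imputation list in SAP 6.1.2.1 is optional and for consistency only. The SAP document history reports just two early discontinuations, so it would change almost nothing. If the primary model can no longer be altered, the extended model can be specified as a sensitivity analysis instead.

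The cost is SAP wording, two variable names in the code and two degrees of freedom (144 to 142), so at worst an interval about 0.7% wider. No new data are needed.
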